1.0 Summary of Study

Background: Total hip arthroplasty (THA) is now the second most common joint replacement surgery in the US due in part to an aging population [1]. Opioid sparing analgesic treatments such as lumbar plexus and femoral nerve blocks are effective but they carry a high risk of undesirable lower limb motor or muscle weakness. Fascia iliaca block, on the other hand, does not consistently provide adequate pain relief [2, 3]. Today, early mobilization, rehabilitation and participation in physical therapy is an integral part of enhanced functional recovery program after THA. Because innervation of the hip joint is complex and preservation of lower extremity motor function is paramount, optimal regional analgesic intervention for THA has yet to be defined [4, 5]. The pericapsular nerve group (PENG) block is a novel regional anesthesia technique for providing analgesia after hip fractures and hip arthroplasties. Quality of recovery scores are patient reported outcome measures evaluating recovery after surgery and anesthesia. The quality of recovery-15 (QoR-15) is a validated questionnaire to assess postoperative recovery (6). The aim of this single center, double blind, randomized controlled trial is to confirm the efficacy of the PENG block for postoperative recovery after primary THA.

Methods: The participants will be randomly assigned to either PENG block group or “no Block” group using a random number generator. The patient will be blinded to the group allocated. The primary outcome will be the quality of recovery 15 score (QoR-15). The secondary outcomes will be visual analog scale score of pain postoperatively, opioid

requirements in first 24 hours, ambulation distance on postoperative day1 and patient satisfaction. Statistical analysis will be performed using the student's t-test, Mann-Whitney U test, and Fisher's exact test as appropriate per sample. A p-value of less than 0.05 will be considered statistically significant.

INTRODUCTION

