9.0 STATISTICAL CONSIDERATIONS

General Data Analysis Plan:

The distribution of the continuous factors will be examined using data visualization techniques such as q-q plots and the Shapiro-Wilk test. All normally distributed demographic and continuous variables will be expressed as means and standard deviations; categorical factors will be expressed as proportions. For non-normal data, the medians and inter quartile ranges will be displayed. For data that are normally distributed, Student's t-test will be used to compare the groups. For data that are not normally distributed, a Mann-Whitney tests will be used for comparisons. Chi-square or Fisher's exact tests will be used to analyze categorical data. Time to event data such as distance of first ambulation will be analyzed using Kaplan-Meier curves. The planned sub-group analysis will be conducted for GA vs. Spinal using a 2x2 ANOVA test. For all comparisons, a value of $p < 0.05$ will be considered statistically significant. Statistical analyses will be performed using SAS for Windows, version 9.2.

Statistical Power and Sample Size Estimates: Fifty-six patients in each group are required to detect a Minimal Clinically Important Difference (MCID) of 8 points for QoR-15 score assuming a standard deviation of 15 points using data from previous studies (19, 20) for 5% significance level and 80% power.

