Data were summarised using means and standard errors (SE) for continuous outcomes or counts and percentages for categorical outcomes. Two-sample t-tests and chi-square tests were used to compare the two groups. Normality for continuous outcomes was assessed using probability plots and the Shapiro-Wilk test for normality. For any outcomes where normality could not be reasonably assumed, medians and interquartile ranges were reported instead of medians and standard errors, respectively, and the Wilcoxon rank sum test was used in place of the t-test. A 95% confidence interval for differences in means (for continuous outcomes) or relative risks (for categorical outcomes) were calculated. For any non-normally distributed continuous outcomes, asymptotic Hodges-Lehmann confidence limits were calculated.¹⁶ A p-value < 0.05 was considered statistically significant. SAS version 9.4 (SAS Institute Inc., Cary, NC) was used to conduct all statistical analyses.

Sample size calculation

A difference of 8 points is widely accepted as a minimal clinically important difference (MCID) for QoR-15 scores for perioperative interventions.¹⁷ A previous study showed a median QoR-15 score of 115 in the control group for the THA population.¹⁸ Assuming an increase to 123 in the QoR-15 score would be clinically relevant and a standard deviation of 15 points, we estimated that fifty-six patients were needed in each group for 80% power at a 5% significance level.

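### Does letting a normality check choose between a t-test and a rank test put the primary 24-hour QoR-15 comparison at risk?

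*Combined protocol and SAP*

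**What the plan says.** Section 6.0 (Measured Outcomes) makes QoR-15 at 24 hours the single primary outcome. Three places cover how it is tested, each in general terms.

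- Section 1.0 lists "student's t-test, Mann-Whitney U test, and Fisher's exact test as appropriate per sample".
- Section 9.0 examines continuous variables with "data visualization techniques such as q-q plots and the Shapiro-Wilk test", sends normal data to Student's t-test, and then states: "For data that are not normally distributed, a Mann-Whitney tests will be used for comparisons".
- The Statistical analysis text after the QoR-15 form has the same switch. The trigger is "For any outcomes where normality could not be reasonably assumed", and the result is that "the Wilcoxon rank sum test was used in place of the t-test".

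On effect measures, section 9.0 gives only descriptive summaries. The appended text provides "A 95% confidence interval for differences in means (for continuous outcomes", a bracket that is not limited to normally distributed outcomes. For non-normal continuous outcomes it adds that "asymptotic Hodges-Lehmann confidence limits were calculated".

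On size, section 9.0 says: "Fifty-six patients in each group are required to detect a Minimal Clinically Important Difference (MCID) of 8 points for QoR-15 score", with an SD of 15, 80% power and a 5% level. The appended Sample size calculation plans a rise from 115 to 123 and takes the 115 from a median in an earlier study.

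**The concern.** A single primary outcome would normally have one named test and one named effect measure. Here both appear to depend on a judgement about the trial's own scores. The plan gives no Shapiro-Wilk threshold and no rule for a plot and a test that disagree. It does not say whether arms, pooled scores or residuals are examined. Two analysts could follow the text and run different tests.

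Three things could be at stake: type I error, if the two-stage choice inflates it; power, since 56 per arm was sized for means; and interpretation, since a mean difference and a Hodges-Lehmann shift need not agree when read against 8 points.

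**Working it through.** **1. The plan's sample size.** Inputs from section 9.0: difference 8, SD 15, 5% level, 80% power. Two-sided testing is assumed because the documents do not state sidedness.

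n per arm = 2 × (1.960 + 0.842)² × 15² / 8² = 55.2, rounded up to 56. This matches. A one-sided test would need 44, which does not match. Noncentral-t power at 56 per arm is 79.9%. So 56 is a two-sided comparison of two means.

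**2. If the rank test is used.** With normal scores its asymptotic relative efficiency is 3/π = 0.955, so n = 55.2 / 0.955 = 57.8, and power at 56 is 78.8%. At the worst-case efficiency for a shift, 0.864, power at 56 is 74.6%. With skewed scores the rank test can be the stronger one.

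**3. The rule as a whole, for shift-type effects.** Simulation with 5,000 trials per scenario and 56 per arm. Score shapes are assumptions, as the documents give no distribution. The rule is taken as Shapiro-Wilk p < 0.05 in either arm leading to Mann-Whitney, otherwise the t-test. The comparator is the unequal-variance t-test.

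| Assumed shape (SD about 15, difference about 8) | Power, t-test | Power, rule | Type I error, rule |
|---|---|---|---|
| Normal, capped at 150 | 78.6% | 78.6% | 5.1% |
| Beta on 0–150 | 79.3% | 82.9% | 5.5% |
| Skew −1 | 79.0% | 84.2% | 5.5% |

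The Monte Carlo standard error on type I error is about 0.3 points, and the t-test itself gave 5.1% to 5.3%. A separate run of 10,000 trials per scenario gave the rule type I error of 4.4% (near-normal) and 5.0% (left-skewed). Its power was 79.6% and 86.3%, against 79.7% for the ordinary t-test in both.

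**4. Discretion within the rule.** Across the three shapes, per-arm, pooled and residual checks at 0.05 do not all pick the same test in 16%, 21% and 8% of trials. Allowing cut-offs of 0.01, 0.05 or 0.10 as well, the figures are 36%, 56% and 27%. A different test is seldom a different conclusion: the significance verdict changes in 0.4% to 0.8% of trials at 0.05, and in 1.1% to 2.4% over all cut-offs.

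**5. Deliberate abuse.** Suppose an analyst always reported the smaller p-value. The false-positive rate is then (t-test rate + rank rate + rate of disagreement) / 2. From the 10,000-trial null runs:

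- near-normal: (4.40 + 4.45 + 1.97) / 2 = 5.4%
- skewed: (4.97 + 4.79 + 2.50) / 2 = 6.1%

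Even this, which the plan does not permit, adds about one point.

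**6. Where the two measures part.** Assume 30% of controls recover poorly, 32 points below the rest, with SD 8.6 within each group. The block lowers that share, and a shift makes up the rest of the 8 points.

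| Poor recoveries on the block | Added shift | Power, t-test | Power, rule | Mean Hodges-Lehmann value |
|---|---|---|---|---|
| 5% | 0 | 83.1% | 62.3% | 5.7 |
| 10% | 1.6 | 80.0% | 70.4% | 6.3 |
| 15% | 3.2 | 75.4% | 74.2% | 6.8 |
| 20% | 4.8 | 73.4% | 77.9% | 7.2 |
| 30% | 8.0 | 69.2% | 77.8% | 8.0 |

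These rows do not share one SD. The control variance is 8.6² + 0.30 × 0.70 × 32² = 289, so the SD is 17.0. The 5% arm has 8.6² + 0.05 × 0.95 × 32² = 122.6, so the pooled SD in the first row is √205.8 = 14.3, against 17.0 in the last.

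**The case for a change.** The strongest case for a change is one of principle. The primary test and estimand should not rest on an undefined judgement made after the outcomes are known, and naming them would take a few sentences and no extra patients. It is supported by the first two rows of the mixture table. A block that truly raises the mean by 8 points could show an average Hodges-Lehmann value near 6 and lose 10 to 21 points of power, so a benefit that meets the MCID on the planned scale might be reported as falling short.

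The absence of a cut-off and of a named test stands. The mixture arithmetic also stands, but only as illustration: no section describes such a distribution, and by the 20% row the advantage has reversed. In the 10% and 15% rows the versions of the normality check disagree in only 1% to 4% of trials and the verdict does not change. There the loss comes from using a rank test at all, not from an unwritten threshold.

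The point about the effect measure is weaker than it looks. The appended text can be read as giving the mean-difference interval for every continuous outcome, with Hodges-Lehmann limits added for non-normal ones. On that reading the figure to set against 8 points is already produced. The median behind the 115 unsettles little, because under a shift the mean, median and Hodges-Lehmann differences are the same.

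Finally, the appended text is in the past tense. If it describes a completed analysis, a new choice there could no longer be called pre-specified.

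**Conclusion.** No change is called for. The plan leaves a threshold unwritten and its effect-measure wording can be read two ways, but an analyst who follows it in any sensible way reaches sound inference. Type I error is 4.4% to 5.5%, shift-type power is 78.6% to 86.3%, and verdicts differ between readings in at most 2.4% of trials.

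Fixing the mean difference would give a cleaner estimand. It would cost about 4 to 5 points of power under skewed shifts (79.3% against 82.9%, 79.0% against 84.2%) and about 9 in the mixture with a pure shift (69.2% against 77.8%). It gains clearly only when the effect is mostly prevention of poor recoveries. Statisticians would differ on that trade.

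The conclusion rests on the assumed score shapes, two-sided testing, a Shapiro-Wilk cut-off of 0.05 for the main runs, and 56 analysed patients per arm. It would weaken if there were evidence that the block acts mainly on the lower tail of QoR-15; the documents give none.

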 - Patient will be followed up until nerve block resolves.
 - Patients' participation in physical therapy will be recorded from physical therapy notes. Specifically, independence in mobility and transfers (independently, with minimal supervision, with moderate supervision, with maximal supervision) and ambulation distance will be recorded using standard PT protocols used at UAB Highlands.
 - The patients will be surveyed regarding their satisfaction with postoperative analgesia. Likert scale will be used to assess their satisfaction level. There will be 4 options to report: very unsatisfied, unsatisfied, satisfied, and very satisfied.
 - The hours from block placement until hospital discharge will be calculated.
- A blinded research associate will evaluate the patients postoperatively to collect data.

Procedure	Length of Time Required of Participants	Frequency of Repetition
Presurgical Evaluation on the day of surgery	30 minutes	once
Randomization on day of surgery	5 minutes	Once
Placement of block	Approximately 30 min.	Once
Post Anesthesia Care Unit (PACU) assessment	10 minutes	Once
First postoperative assessment survey (approximately 24 hours after surgery)	20 minutes	Once

Second postoperative assessment survey (approximately 48 hours after surgery)	10 minutes	Once
--	-------------------	-------------

- Measured Outcomes:

- Primary outcome:
 - Quality of Recovery after surgery assessed on postoperative day 1 (at 24 hours).
QoR-15 scale (form attached) will be used to assess post-operative recovery based on 15 questions: scores will range from 0-150, 0 being the worst recovery and 150 being the best (excellent) recovery.
- Secondary outcomes:
 - QoR-15 at 48 hours
 - VAS scores (0-10) at immediate postoperatively, 6, 12 and 24 hours at rest and movement. VAS score 0 indicates “no pain” and 10 indicates “worst pain experienced”. Highest pain score in first 24 hours will be recorded.
 - Opioid consumption intraoperatively, as well as at 24 hours postoperatively. Oxycodone PO and Hydromorphone iv usage in first 24 hours postoperatively.
 - Incidence of nausea, vomiting and itching in first 24 hours postoperatively.
 - Physical therapist assessment of independence in mobility and transfers (independent, with minimal supervision, with moderate supervision, with maximal supervision)

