 - Physical therapist documentation of ambulation distance
 - Patient satisfaction on Likert scale will be used to assess their satisfaction level. There will be 4 options to report: very unsatisfied, unsatisfied, satisfied, and very satisfied.
 - Hours to hospital discharge (Surgery finish time to discharge time).

List of variables/data points you will be collecting (e.g. – age, gender, date of surgery, etc.):

We will collect the following data:

1. patient age
2. patient gender

3. Weight
4. Height

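### Two four-level ordered secondary outcomes fall under the chi-square/Fisher rule, which ignores their order, and the relative risk has no stated split

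*Combined protocol and SAP*

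**What the plan says.** Under Measured Outcomes in section 6.0, satisfaction is a four-point scale: "There will be 4 options to report: very unsatisfied, unsatisfied, satisfied, and very satisfied". The same list includes "Physical therapist assessment of independence in mobility and transfers", also with four levels, from independent to maximal supervision. Both serve objective 2 in section 3.0.

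No part of the document assigns a test to either outcome by name. The general rules are:

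- **Section 1.0 (Methods):** t-test, Mann-Whitney and Fisher's "exact test as appropriate per sample".
- **Section 9.0 (General Data Analysis Plan):** "categorical factors will be expressed as proportions", and chi-square or Fisher's "exact tests will be used to analyze categorical data". Mann-Whitney is for data that are not normally distributed, in a paragraph that opens with continuous factors.
- **Statistical analysis text after the QoR-15 form:** "Two-sample t-tests and chi-square tests were used to compare the two groups". Where normality fails, "the Wilcoxon rank sum test was used in place of the t-test". For effect measures, "A 95% confidence interval for differences in means (for continuous outcomes) or relative risks (for categorical outcomes) were calculated".

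No trend test, ordinal model or cut-point appears anywhere.

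**The concern.** Chi-square and Fisher's exact test treat the four levels as unordered labels. They ask whether the two distributions differ in any way, not whether one arm does better. The trial's hypothesis is directional (better recovery with the block), and the effect one would expect on these scales is a general move towards more satisfaction and more independence. An unordered test spreads its sensitivity over three degrees of freedom and is less likely to detect such a move. Readers could see the direction in the proportions, but the p-value would not test it.

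The relative risk raises a separate problem. A four-level scale has three possible splits into better and worse. Since none is written down, the split could be chosen after the results are seen, and the same shift could be reported as almost nothing or as a large benefit.

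**Working it through.** **The plan's own figure.** The only sample size in the documents is for the primary outcome, QoR-15 at 24 hours: difference 8, SD 15, 5% significance (taken as two-sided), 80% power. n = 2 × (1.960 + 0.842)² × 15² / 8² = 2 × 7.85 × 225 / 64 = 55.2, so 56 per group, as stated. It supplies the n used below; the documents state no figure for the two ordered outcomes.

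**Does chi-square ignore order?** Take an invented table with 56 per arm, worst level to best: control 3/8/25/20, PENG 1/4/20/31.

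- Chi-square with equal arms is the sum of (difference)² / (level total): 4/4 + 16/12 + 25/45 + 121/51 = 1.00 + 1.33 + 0.56 + 2.37 = 5.26 on 3 df, p = 0.154. Shuffling the level labels leaves this unchanged.
- Rank-sum: the mid-ranks of the four levels are 2.5, 10.5, 39 and 87. The PENG rank sum is 1×2.5 + 4×10.5 + 20×39 + 31×87 = 3521.5, against an expected 56 × 113 / 2 = 3164. The tie-corrected variance is (56²/12) × (113 − 225456/12432) = 24,791, SD 157.5, so z = 357.5/157.5 = 2.27 and p = 0.023.

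**Power.** Two control distributions are assumed, worst level to best: A = 5/15/50/30% and B = 25/35/25/15%. The PENG arm is shifted by a common (proportional) odds ratio. Trials of 56 per arm were simulated, with two-sided 5% tests, Fisher's test by full enumeration of the 2×4 table, and Wilcoxon corrected for ties.

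| Odds ratio | A: chi-square / Fisher / Wilcoxon | B: chi-square / Fisher / Wilcoxon |
|---|---|---|
| 2.0 | 32 / 34 / 49% | 36 / 36 / 52% |
| 2.5 | 53 / 56 / 71% | 59 / 59 / 76% |
| 3.0 | 71 / 74 / 86% | 76 / 76 / 89% |

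With no effect, all three tests reject in about 4 to 5% of trials. The loss against Wilcoxon is 12 to 18 points, and Fisher's test does not recover it. To match Wilcoxon at 56 per arm, chi-square would need about 78 to 86 per arm. Four other assumed control distributions (5/15/45/35, 10/20/40/30, 25/25/25/25 and 3/7/40/50%) gave a similar loss for chi-square, about 12 to 19 points. At a smaller odds ratio of 1.5 the loss is about 7 to 8 points, and neither test has useful power (chi-square about 13 to 15%, Wilcoxon about 21 to 22%).

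**Relative risk by split.** Let p be the control proportion on the better side of a split. With odds ratio 2.0 the PENG proportion is q = 2p / (1 + p), and the relative risk is q/p = 2 / (1 + p).

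- A: p = 0.95, 0.80, 0.30 gives 2/1.95 = 1.03, 2/1.80 = 1.11, 2/1.30 = 1.54.
- B: p = 0.75, 0.40, 0.15 gives 2/1.75 = 1.14, 2/1.40 = 1.43, 2/1.15 = 1.74.

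**A case that goes the other way.** If the block moved patients towards both extremes (A changing to 10/20/25/45%), chi-square has about 65% power and Wilcoxon about 8%.

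**The case against.** The strongest reply is that the plan never commits these outcomes to chi-square. The Mann-Whitney sentence in section 9.0 speaks of data, not of continuous variables, and the summary leaves the choice open, so an analyst who scored the scales 1 to 4 and used Mann-Whitney could claim to follow the plan. This is fair as far as it goes: the assignment is by general rule only. But the section 9.0 paragraph is framed around continuous factors, and the later text puts Wilcoxon in place of the t-test, not of chi-square. If the looser reading were accepted, the plan would allow two tests for the same outcome, which needs the same correction.

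Second, chi-square and Fisher's test are valid and do better when the difference is not a consistent shift. This stands. The gain depends on the pattern of effect, which is why the four proportions should still be shown.

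Third, the magnitude rests on distributions and odds ratios that are not in the documents, and the trial was powered only for QoR-15. This also stands: the 12 to 18 points belong to odds ratios of 2 to 3, and the figure of 78 to 86 per arm measures inefficiency and is not a shortfall in recruitment.

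Fourth, the relative-risk sentence is generic and may have been meant for nausea, vomiting and itching. That is possible, but it is written for categorical outcomes without exception and gives no split.

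**Conclusion.** The concern holds. On the natural reading, two ordered outcomes that serve objective 2 go to tests that ignore order, and the named effect measure is undefined for them until a split is chosen. For a consistent shift with an odds ratio between 2 and 3, the cost is about 12 to 18 points of power at 56 per arm, given the assumed control distributions; it is smaller for weaker effects and reverses if the effect is not monotone. One and the same shift can appear as a relative risk of 1.03 or 1.54. The primary QoR-15 analysis, the sample size and the type I error rate are unaffected. It should be corrected, but it does not threaten the trial's main conclusion.

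**What to change.** State that satisfaction and independence in mobility and transfers are compared with the Wilcoxon rank-sum test, which the plan already uses elsewhere. Report a proportional-odds common odds ratio with 95% CI, next to the four proportions per arm so that a non-monotone pattern would be visible. Keep chi-square or Fisher's test and the relative risk for nausea, vomiting and itching. If a relative risk is wanted for either ordered scale, fix the split in advance.

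Before analysis this costs only wording, with the same data and software. The price is reliance on a roughly consistent shift. The Statistical analysis text is in the past tense, so the data may already have been analysed; in that case the ordinal analysis should be labelled post hoc.

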5.0 RANDOMIZATION/RECRUITMENT DETAILS (If applicable)

- Randomization groups, how will subjects be randomized:

Upon enrollment in the study, participants will be randomized 1:1 to either the investigational group (“PENG Block” group) or the control group (“No Block” group). Participants will be randomized using a random number generator. The randomization will be performed using computer-generated random numbers. The study will follow a 1:1 allocation ratio for the intervention (PENG) and control (No-PENG). A random permuted block will be used to reduce the predictability of allocation. The randomization sequence will be generated using computer software using a block randomization method where blocks are variable in size (minimum block size four). The study will use a sealed opaque envelope as method to comply with allocation concealment.

- Blinded Yes No (Single Double please check box).
- Participants and outcome assessors will be blinded. The anesthesiologist performing the block will not be blinded to the group allocation.

6.0 **STUDY INTERVENTIONS/PROCEDURES**

All patients will receive standard pre-operative dose of 1000 mg of acetaminophen, and 200 mg of celecoxib as multimodal analgesia regimen.

- Study design:[Click here to enter text.](#)
 - Participants in the study will be blinded to their treatment group. All patients will receive acetaminophen 975 mg PO and celecoxib 200 mg PO. Dose of celecoxib will be adjusted based on renal function, and no celecoxib will be given for GFR < 30 ml/min.
 - Participants in the pericapsular nerve group block (PENG) arm will receive a PENG block preoperatively in the block area placed under direct ultrasound guidance as follows:
 - Patients will be placed in the supine position resting comfortably. Standard noninvasive monitors will be applied, and oxygen will be administered via nasal cannula. Parenteral midazolam and fentanyl will be titrated to patient comfort. Standard skin sterilization, prepping and draping will be applied to the area. Anatomical landmarks identified using ultrasound and skin will be numbed using 2-3 cc of 2% lidocaine. Long acting local anesthetic, a bolus of 25 cc of 0.5 % Bupivacaine will be injected lateral to iliopubic eminence (IPE). A Curvilinear low frequency (2-5 MHz) ultrasound probe will be used to identify landmarks. A 22 G, 10 cm needle will be inserted using in-plane technique and advanced to target site (17).

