 - After the PENG block is placed, patients will have THA under spinal or general anesthesia. Spinal anesthesia will be provided by intrathecal injection of hyperbaric (0.75%) bupivacaine. General anesthesia will be provided by propofol induction, rocuronium for muscle relaxation and inhalation anesthetics for maintenance. Patients will receive fentanyl 25-50 mcg iv for increase in systolic blood pressure (SBP) > 25% of baseline SBP. Intraoperatively patients will also receive 4mg dexamethasone iv and 4 mg ondansetron iv.
 - Control group participants will be transferred to the block area preoperatively, and care will proceed as if they were receiving injection.
 - Patients will be placed in the supine position resting comfortably. Standard noninvasive monitors will be applied, and oxygen will be administered via nasal cannula. Parenteral midazolam and fentanyl will be titrated to patient comfort. Standard skin sterilization, prepping and draping will be applied to the area. The ultrasound probe will be used to

identify the iliopubic eminence (IPE). Only skin will be numbed using 2-3 cc of 2% lidocaine and NO bolus of bupivacaine will be injected.

- Postoperative patients in both the PENG arm and the control arm will be given scheduled PO acetaminophen 975 mg BID, and celecoxib 200mg BID (Dose of celecoxib will be adjusted based on renal function, and no celecoxib will be given for GFR < 30 ml/min) as part of multimodal pain regimen. Patients will be given a standard pain regimen of PRN Oxycodone 5 mg Q 4 hours for breakthrough pain, and hydromorphone 1mg IV every 6 hours prn as rescue analgesia for severe pain (NRS score more than 7/10). Patients will get prn ondansetron 4 mg iv every 4 hours. Naloxone iv prn will be used for any opioid related itching or respiratory depression.
- The following data will be collected
 - Quality of recovery (QoR) survey will be filled on post-operative day at 24 and 48 hours.
 - Patients will be evaluated immediately post-operatively in PACU, and 6, 12 and 24 hours post-surgery to determine VAS pain scores at rest and movement on the scale of 0-10. Also highest pain score during first 24 hours will be recorded.
 - Twenty-four hour opioid consumption will be calculated with respect to 24 hours oxycodone use and 24 hours hydromorphone use.
 - Data for postoperative use of ondansetron and naloxone will be collected. Also any postoperative episodes of nausea, vomiting, and itching will also be recorded.

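### Does the GA-versus-spinal subgroup need to be defined by the planned rather than the received anaesthetic?

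*Combined protocol and SAP*

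**What the plan says.** The General Data Analysis Plan in section 9.0 contains one sentence on the subgroup: "The planned sub-group analysis will be conducted for GA vs. Spinal using a 2x2 ANOVA test". Here the word planned describes the analysis, not the anaesthetic, so it does not settle the definition. The Statistical analysis section after the QoR-15 form, at the end of the document, does not mention the subgroup.

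On timing, section 5.0 says "Upon enrollment in the study, participants will be randomized 1:1 to either the investigational group", and the procedure table in section 6.0 lists "Presurgical Evaluation on the day of surgery" followed by "Randomization on day of surgery". Concealment is by envelope: "The study will use a sealed opaque envelope as method to comply with allocation concealment". Section 6.0 then says "After the PENG block is placed, patients will have THA under spinal or general anesthesia". No section says who chooses between the two, when the choice is fixed, or how a change from one to the other is classified.

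On blinding, section 5.0 says "The anesthesiologist performing the block will not be blinded to the group allocation", while patients and outcome assessors are blinded. For the control arm, section 6.0 says "Control group participants will be transferred to the block area preoperatively, and care will proceed as if they were receiving injection".

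The numbered list of data points at the end of section 6.0 includes surgical approach and ASA status but not anaesthetic type.

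**The concern.** A subgroup factor fixed before allocation is balanced by randomisation, so the arm comparison within each level is a fair one. A factor realised after allocation has that protection only if arm does not affect it. Here the anaesthetic is delivered after the block, and at least one anesthesiologist knows the allocation. Suppose that person, knowing a patient had no block, moved some frailer or more anxious control patients from spinal to GA. The control patients left in the spinal group would then look better than their PENG counterparts, and those in the GA group worse. The 2x2 ANOVA could show a block-by-anaesthetic interaction that does not exist.

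A note of the intended type made before the envelope is opened would remove this possibility, and it cannot be created afterwards. Two analysts could also class a converted patient differently and both comply with the plan. What is at stake is the reading of this one subgroup; the comparison of whole arms does not use the anaesthetic at all.

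**Working it through.** **Inputs from the documents (section 9.0):** SD 15 points, difference 8 points, 56 per group, 5% significance, 80% power.

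**The plan's own figure.** n per group = 2 × 15² × (1.960 + 0.842)² / 8² = 55.2, rounded up to 56. The stated size reproduces with a two-sided test. The definition of the subgroup does not enter it.

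**Precision of the subgroup.** The documents give no GA share, so 60% spinal is assumed, with 30% and 80% as the range. With 56 per arm, 60% spinal gives 33.6 spinal and 22.4 GA patients per arm.
- SE of the interaction = 15 × √(2/33.6 + 2/22.4) = 15 × 0.3858 = 5.79 points.
- 95% half-width = 1.98 × 5.79 = 11.5 points (t with 108 df).
- Power for a true 8-point interaction (noncentral t) = 27.8%. It is 24.9% at 30% spinal and 20.1% at 80%.

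**Size of a spurious interaction under received type.** Everything here beyond SD 15 and 56 per arm is assumed: no true block effect, equal mean prognosis in the two planned-type groups, only control patients switching and only from spinal to GA, and correlation r between the clinician's judgement and 24-hour QoR-15.

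Let q = share of controls switching / planned-spinal share, and let φ be the normal density at the q-th quantile.
- Mean prognosis of controls who stay spinal = 15 r φ / (1 − q).
- Mean prognosis of switchers = −15 r φ / q.
- Apparent block effect under spinal = minus the stayers' mean.
- Apparent block effect under GA = minus (switch share × switchers' mean) / (GA share + switch share).

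Worked case, 60% spinal, 10% switching, r = 0.3: q = 0.10/0.60 = 0.167, φ = 0.2499.
- Stayers: 15 × 0.3 × 0.2499 / 0.833 = 1.35, so the effect under spinal is −1.35.
- Switchers: −15 × 0.3 × 0.2499 / 0.167 = −6.75, so the effect under GA is 0.10 × 6.75 / 0.50 = +1.35.
- Spurious interaction = 1.35 − (−1.35) = 2.70 points; SE with switching 5.73.

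Results at 60% spinal:

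| r | 5% / 10% / 15% of controls switch (points) | Rejection rate of the 5% test |
|---|---|---|
| 0.2 | 1.1 / 1.8 / 2.3 | 5.4 to 6.8% |
| 0.3 | 1.7 / 2.7 / 3.5 | 6.0 to 9.2% |
| 0.45 | 2.5 / 4.0 / 5.2 | 7.2 to 14.6% |

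The largest value in the table, 5.2, is 0.91 of its SE (5.74). Over planned-spinal shares of 30 to 80% the worst rejection rate is 16.2%, at 80% spinal with r = 0.45 and 15% switching; there the bias is 6.4 against an SE of 6.5.

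**What drives it.** The result needs one-sided switching. In 8,000 simulated trials with the same switching in both arms (r = 0.45, 10%), the mean interaction was −0.01 with 5.4% rejection. The whole-arm difference stayed within 0.07 of zero in every scenario.

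**Cost of using planned type.** If 10 of every 60 planned-spinal patients in both arms switch regardless of prognosis, a true 8-point interaction appears as 8 × (1 − 10/60) = 6.7 points, and power at SE 5.79 falls from 27.8% to 20.8%.

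**The case for a change.** The best case for acting is that the remedy is nearly free. A presurgical evaluation is listed ahead of randomisation and allocation sits in an envelope, so one tick-box, one field for the actual type and one SAP sentence would remove the ambiguity without limiting clinical choice. The intended type cannot be recovered later, whereas the anaesthesia record would give only the received type. Section 9.0 also applies p<0.05 to every comparison, so an interaction would be called significant or not with no exploratory label.

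The textual part stands: the definition is unwritten. The rest carries less weight.
- The documents date the delivery of the anaesthetic, not the choice. They do not say that the anesthesiologist who places the block selects it, and the control arm goes through the same block-area preparation.
- Absence from the data list is weak evidence that anaesthetic type goes unrecorded. The same list omits QoR-15 itself, satisfaction, nausea and the 6- and 12-hour pain scores, all collected elsewhere in section 6.0.
- Planned type is the safer definition in principle, but it dilutes a true interaction when patients switch.
- Reporting an interval rather than a p-value verdict is a reasonable preference, but it is a separate matter from how the factor is defined.
- The closing statistical section is in the past tense. If it describes a finished analysis, a pre-allocation record is no longer possible.

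**Conclusion.** No change to the plan is needed. Section 9.0 leaves the subgroup factor undefined, but read with section 6.0 it most naturally means the anaesthetic received, and that reading is sound unless the choice depends on arm and is related to prognosis. The documents establish neither condition. The bias figures of 1.1 to 5.2 points rest on assumed control-only switching, an assumed 60% spinal share and assumed correlations of 0.2 to 0.45. They remain below one standard error, and disappear when switching is alike in the two arms.

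The gain would also be small. No objective or hypothesis in section 3.0 concerns anaesthetic type, and with about 28% power and an interval of about ±11.5 points (again at 60% spinal) the subgroup could not settle the question under either definition. The primary 24-hour QoR-15 comparison and its 56 per group are unaffected. A team that has not begun enrolment could note the intended type as good practice; omitting it is a gap in detail, not a fault in the design.
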